5.7 Treatment Compliance

Individual subject compliance in taking study drug will be monitored by counting unused medication returned by the subject at visits. Compliance will be documented. If compliance is less than 80% or more than 120%, the Investigator or designee is to counsel the subject and ensure that steps are taken to improve compliance. Subjects who are less than 80% or more than 120% compliant with the dosage regimen for any 2 consecutive visit periods during the study may be withdrawn from the study.

5.8 Prior and Concomitant Medications

The Investigator or designee must record the use of prior medications (all medication taken within 30 days prior to Visit 1) and current treatment (including both drug and nondrug therapies and all prescribed, over-the-counter [OTC], and alternative medicines) in the eCRFs. The minimum requirement is that the drug name and dates of administration are to be recorded. This also includes drugs used on a chronic or as-needed basis. Subjects must be instructed not to start any new medication, either prescribed or OTC, without consulting the Investigator, unless the new medication is required for emergency use. Subjects must be instructed to notify the Investigator immediately if medications are required for emergency use.

Any changes in concomitant medications also will be recorded in the subject's eCRF.

Any concomitant medication deemed necessary for the welfare of the subject during the study may be given at the discretion of the investigator. However, it is the responsibility of the investigator to ensure that details regarding the medication are recorded in full in the eCRF.

5.8.1 Prohibited Concomitant Medications and Treatments

Prohibited medications and treatments during the study duration include the following:

- Systemic hormonal products including but not limited to estrogens, progestins, testosterone, methyltestosterone, oxandrolone (Oxandrin[®]), oxymetholone, danazol, fluoxymesterone (Halotestin[®]), other androgenic compounds, including herbals such as fenugreek, Korean ginseng, goat weed, forskolin, ashwagandha, and Testro-X[®]. Intravaginal application of estradiol topical/tablet agents and hormones delivered via vaginal ring are allowed.
- Any new treatment (medication or otherwise), including vaginal rejuvenation, that is known or suspected to affect lower urinary tract function throughout the treatment and follow-up periods
- Treatment with any investigational agent within the 30 days before the first dose of study treatment
- New pelvic floor exercises (including Kegel) throughout the treatment and follow-up period

6 Study Assessments and Procedures

Before performing any study procedures, all potential subjects will sign an informed consent form (ICF). Subjects will have the opportunity to have any questions answered before signing the ICF. The investigator must address all questions raised by the subject. The investigator will also sign the ICF.

6.1 Study Visits

The schedule of events for this study is presented in Table 12–1.

6.1.1 Screening

6.1.1.1 Screening Visit, Days –28 to 0

The study will be explained in detail and adequate time will be allowed for answering questions from a potential subject before she signs the institutional review board (IRB)-approved informed consent document. Informed consent will be obtained from those potential subjects meeting initial inclusion/exclusion criteria and expressing willingness to participate before study site personnel conduct any study assessments of such subjects.

Once informed consent is obtained, a subject number will be assigned and a detailed interview will be conducted with the subject about her medical history, including past gynecological and obstetric history (gravida, para, prior abortions and deliveries) and about her concomitant medications. The subject will complete the MESA incontinence questionnaire to determine if she has predominant stress incontinence. If the urinary continence type is stress predominant, a BST will be conducted to confirm SUI. Height and weight will be measured, and vital signs will be assessed. A gynecologic pelvic examination and a physical examination will be conducted. A dipstick urinalysis will be performed and blood will be drawn for laboratory tests as presented in Table 12–1. The subject's eligibility criteria will be reviewed and, if the subject is considered to be provisionally qualified, she will undergo the additional screening procedures described in Section 6.1.1.2.

6.1.1.2 Additional Screening Procedures

If the subject has provisionally qualified for the study during the Screening Visit, the following procedures will be performed between the Screening Visit and Visit 1 (Baseline):

- A mammography examination will be performed, unless the subject provides evidence of a mammography examination performed within the 6 months prior to the Screening Visit
- A transvaginal ultrasound examination will be performed in subjects with an intact uterus
- A 12-lead electrocardiography examination will be performed
- The subject will complete a 24-hour pad weight test
- The subject will complete a 3-day voiding diary

6.1.2 Study Visit 1: Week 0, Clinic Visit

Concomitant medications and AEs will be reviewed. The results of the 24-hour pad weight test and the 3-day voiding diary will be reviewed, and continued eligibility for enrollment will be evaluated, also considering the results of laboratory tests during screening. A subject meeting the inclusion and exclusion criteria after all screening study measures have been completed and reviewed will be randomly assigned to treatment (randomization).

Vital signs will be obtained, a dipstick urinalysis will be performed, and the subject will complete the UDI-6, IIQ-7 Short Form, I-QOL, FSFI, PGI-S, and Vaizey Incontinence Severity questionnaires.

Study drug will be dispensed with administration instructions, and each package will be preprinted with a medication identification number. The medication identification number assigned to the subject will be noted in the eCRF for study drug. The subject will take the first dose of study drug during this visit.

6.1.3 Study Visit 2: Week 1, Phone Visit

Approximately 1 week after beginning treatment, the subject will be contacted by phone to assess for concomitant medications and AEs (which will be recorded in the eCRF). The subject will be instructed to complete a 24-hour pad weight and 3-day voiding diary within the week preceding her next study visit. The subject will be reminded to bring all unused study drug (in its original packaging) to her next clinic visit.

6.1.4 Study Visit 3: Week 4, Clinic Visit

Approximately 4 weeks after beginning treatment, the subject will return to the study site for a clinic visit. Unused study drug will be collected. Concomitant medications and AEs will be reviewed. Weight and vital signs will be measured, and a physical examination will be performed. A dipstick urinalysis will be performed, and blood will be drawn for a comprehensive metabolic panel (CMP). Completion of a 24-hour pad weight test and a 3-day voiding diary will be verified.

The subject will complete the UDI-6, IIQ-7 Short Form, I-QOL, FSFI, PGI-S, PGI-I, and Vaizey Incontinence Severity questionnaires.

Study drug will be dispensed with administration instructions, and each package will be preprinted with a medication identification number. The medication identification number assigned to the subject will be noted in the eCRF for study drug.

The subject will be instructed to complete a 24-hour pad weight and 3-day voiding diary within the week preceding her next study visit. The subject will be reminded to bring all unused study drug (in its original packaging) to her next clinic visit.

6.1.5 Study Visit 4: Week 8, Clinic Visit

Approximately 8 weeks after beginning treatment, the subject will return to the study site for a clinic visit. Unused study drug will be collected. Concomitant medications and AEs will be reviewed. Weight and vital signs will be measured, and a physical examination will be performed. A dipstick urinalysis will be performed, and blood will be drawn for a CMP. Completion of a 24-hour pad weight test and a 3-day voiding diary will be verified.

The subject will complete the UDI-6, IIQ-7 Short Form, I-QOL, FSFI, PGI-S, PGI-I, and Vaizey Incontinence Severity questionnaires.

Study drug will be dispensed with administration instructions, and each package will be preprinted with a medication identification number. The medication identification number assigned to the subject will be noted in the eCRF for study drug.

The subject will be instructed to complete a 24-hour pad weight and 3-day voiding diary within the week preceding her next study visit. The subject will be reminded to bring all unused study drug (in its original packaging) to her next clinic visit.

6.1.6 Study Visit 5: Week 12 or Early Withdrawal, Clinic Visit

Approximately 12 weeks after beginning treatment, the subject will return to the study site for a clinic visit. Unused study drug will be collected and accounted for. Concomitant medications and AEs will be reviewed. Weight and vital signs will be measured, and both a gynecologic pelvic examination and a physical examination will be performed. A dipstick urinalysis will be performed and blood will be drawn for laboratory testing as presented in Table 12–1. Completion of a 24-hour pad weight test and a 3-day voiding diary will be verified. A BST and, in subjects with an intact uterus, a transvaginal ultrasound examination will be performed.

The subject will complete the MESA, UDI-6, IIQ-7 Short Form, I-QOL, FSFI, PGI-S, PGI-I, and Vaizey Incontinence Severity questionnaires.

The subject will be instructed to complete a 24-hour pad weight and 3-day voiding diary within the week preceding her next study visit.

6.1.7 Study Visit 6: Week 16, Clinic Visit

Approximately 16 weeks after beginning treatment and 4 weeks after the last dose of study drug, the subject will return to the study site for a clinic visit. Concomitant medications and AEs will be reviewed. Weight and vital signs will be measured, and a physical examination will be performed. Blood will be drawn for laboratory testing as presented in Table 12–1. Completion of a 24-hour pad weight test and a 3-day voiding diary will be verified.

The subject will complete the UDI-6, IIQ-7 Short Form, I-QOL, FSFI, PGI-S, PGI-I, and Vaizey Incontinence Severity questionnaires.

Subjects continuing to Week 20 will be instructed to complete a 24-hour pad weight and 3-day voiding diary within the week preceding her next study visit.

6.1.8 Study Visit 7: Week 20, Clinic Visit

Approximately 20 weeks after beginning treatment and 8 weeks after the last dose of study drug, the subject will return to the study site for a clinic visit. Concomitant medications and AEs will be reviewed. Blood will be drawn for laboratory testing as presented in Table 12–1. Completion of a 24-hour pad weight test and a 3-day voiding diary will be verified.

The subject will complete the UDI-6, IIQ-7 Short Form, I-QOL, FSFI, PGI-S, PGI-I, and Vaizey Incontinence Severity questionnaires.

The subject will be instructed to complete a 24-hour pad weight and 3-day voiding diary within the week preceding her next study visit.

6.1.9 Study Visit 8: Week 28, Clinic Visit

Approximately 28 weeks after beginning treatment and 16 weeks after the last dose of study drug, the subject will return to the study site for a clinic visit. Concomitant medications and AEs will be reviewed. Blood will be drawn for laboratory testing as presented in Table 12–1. Completion of a 24-hour pad weight test and a 3-day voiding diary will be verified.

The subject will complete the UDI-6, IIQ-7 Short Form, I-QOL, FSFI, PGI-S, PGI-I, and Vaizey Incontinence Severity questionnaires.

6.2 Efficacy Assessments

Efficacy assessments will include a 3-day voiding diary, PGI-S, PGI-I, UDI-6, IIQ-7, I-QOL, FSFI, Vaizey Incontinence Severity Score, and 24-hour pad weight test. Changes in subject-reported impressions will be noted.

6.2.1 Three-Day Voiding Diary

Subjects will record all urinary voids, specifying each episode of urinary leakage including type. Fluid intake will also be recorded as well as any episode of vaginal discharge or spotting.

In each 3-day voiding diary, subjects are to record voiding data for 3 consecutive days in a paper diary. To be considered valid, each 3-day voiding diary must be recorded within 7 days on either side of a planned visit, based on the date of randomization.

Three-day voiding diaries are reliable measures of the mean number of urinary incontinence episodes per day, incontinence type, mean voids per 24 hours, and mean voids during sleeping hours.

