7.1 Primary Efficacy Endpoint

The primary efficacy endpoint is a responder analysis, where a responder is defined as having a $\geq 50\%$ reduction at the end of treatment (Week 12) compared to baseline in the mean number of stress incontinence episodes per day as assessed by the 3-day voiding diary. Subjects who have missing diary data for the Week 12 visit will be counted as non-responders for this analysis. Rules for recording valid diary data are presented in Section 6.2.1.

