7.5 Analysis Sets

Data analysis will be performed on a full analysis set (FAS), a per protocol set (PPS), an intent-to-treat (ITT) set, a durability set (DS), and a safety analysis (SA) set.

The FAS is used for the primary analysis. The FAS consists of all randomized subjects who receive at least 1 dose of study drug and have at least 1 post baseline primary efficacy assessment (3-day voiding diary). All analyses using the FAS will group participants according to randomized treatment.

The PPS is used for a supportive analysis and will be defined as all subjects included in the FAS who do not have any significant protocol deviations. All analyses using the PPS will group subjects according to treatment actually received.

The ITT set consists of all randomized subjects who receive at least 1 dose of study drug. All analyses using the ITT set will group subjects according to randomized treatment. Subjects who do not have any postbaseline assessments will be treated as non-responders for ITT analyses.

The DS is used for exploratory analyses to assess the durability of the effect of treatment and will be defined as all subjects who complete a Week 12 final visit and a Week 16, Week 20, or Week 28 assessment.

The SA set contains all subjects randomized in the study who receive at least 1 dose of study drug. All analyses using the SA set will group subjects according to treatment actually received.

All efficacy analyses performed on the FAS will be repeated on the PPS and the ITT set. Further details will be provided in the SAP.

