7.7 Statistical Analysis Methodology

Before unblinding, a separate SAP will be finalized, providing detailed methods for all endpoints. In general, summary statistics (n, mean, standard deviation, median, minimum and maximum values for continuous variables, and number [%] of subjects in each category for categorical variable) will be provided by treatment group and visit. Source data for summary tables and statistical analyses will be presented as subject data listings.

All statistical analyses will be performed using SAS (v9.4 or higher). Unless stated otherwise, all statistical tests will be 2-sided using a 5% significance level, leading to 95% (2-sided) confidence intervals. No adjustment will be made for multiplicity due to 2 dose levels of GTx-024 being compared with placebo. The trial is not powered to show a statistical difference between the 2 dose arms of GTx-024.

The primary efficacy period is defined as baseline (Day 0) through Week 12. Change from baseline and determination of responder rate status will be between baseline and visits through Week 12. The durability period is defined as Week 12 to Week 16, Week 20, and/or Week 28.

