7.7.1 Analysis of the Primary Efficacy Endpoint

The primary analysis will be conducted on the primary endpoint using the FAS.

The primary efficacy endpoint (i.e., a binary response indicator where a responder is defined as having a $\geq 50\%$ reduction at the end of treatment compared to baseline in the mean number of stress incontinence episodes per day as assessed by the 3-day voiding diary) will be evaluated using a logistic regression model. The logistic regression model will include treatment group as a covariate. The odds ratio of response between each dose level of GTx-024 and placebo (together with the corresponding 95% confidence interval) will be reported. The null hypothesis is that there is no treatment effect for either dose level of GTx-024. This will be tested against the alternative hypothesis that there is a treatment effect for at least 1 of the dose levels of GTx-024.

The corresponding *P*-value for the comparison between each dose level of GTx-024 and placebo will be derived using the standard normal distribution. Subjects who have missing diary data for the screening period or the Week 12 visit will be counted as non-responders for this analysis.

Sensitivity analyses will be specified in the SAP.

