12.1 Appendix: Schedule of Events

Table 12–1 Schedule of Events for Protocol G201002

Procedure	Screening Visit	Additional Screening Procedures	Baseline V1	V2 ^a	V3	V4	V5	V6	V7 and V8
Day or Week	Days –28 to 0	Days –28 to 0	Week 0	Week 1	Week 4	Week 8	Week 12 or Early Withdrawal	Week 16 or 30 days after last dose of study drug	Weeks 20 and 28
Visit Window (days)	–	–	–	±3	±3	±3	±3	±3	±3
Informed consent	X								
Eligibility criteria review	X		X						
Medical history	X								
Concomitant medications	X		X	X	X	X	X	X	X
MESA incontinence questionnaire	X						X		
Bladder stress test	X						X		
Height ^b and weight	X				X	X	X	X	
Vital signs	X		X		X	X	X	X	
Pelvic examination	X						X		
Physical examination	X				X	X	X	X	
UA dipstick (with culture as needed)	X		X		X	X	X		
CMP (Chem 14 panel) ^c	X				X	X	X	X	
Viral serology ^d	X								
Serum FSH	X								
CBC	X						X	X	
Lipid panel	X						X	X	X
C-reactive protein (CRP)	X						X	X	
Hormone panel	X						X	X	X

Procedure	Screening Visit	Additional Screening Procedures	Baseline V1	V2 ^a	V3	V4	V5	V6	V7 and V8
Day or Week	Days –28 to 0	Days –28 to 0	Week 0	Week 1	Week 4	Week 8	Week 12 or Early Withdrawal	Week 16 or 30 days after last dose of study drug	Weeks 20 and 28
Visit Window (days)	–	–	–	±3	±3	±3	±3	±3	±3
SHBG	X						X	X	X
Mammography ^e		X							
Transvaginal ultrasound ^f		X					X		
Electrocardiography		X							
24-Hour pad weight test		X			X	X	X	X	X
3-Day voiding diary		X			X	X	X	X	X
Randomization			X						
Adverse event reviews			X	X	X	X	X	X	X
UDI-6			X		X	X	X	X	X
IIQ-7 Short Form			X		X	X	X	X	X
I-QOL			X		X	X	X	X	X
FSFI			X		X	X	X	X	X
PGI-S			X		X	X	X	X	X
PGI-I					X	X	X	X	X
Vaizey Incontinence Severity Score			X		X	X	X	X	X
Dispense study drug			X		X	X			
Collect unused study drug					X	X	X		

Abbreviations: CBC, complete blood count; CMP, comprehensive metabolic panel; FSFI, Female Sexual Function Index; FSH, follicular-stimulating hormone; IIQ-7, Incontinence Impact Questionnaire; I-QOL, Incontinence Quality of Life questionnaire; MESA, Medical, Epidemiological, and Social Aspects of Aging; PGI-I, Patient Global Impression of Improvement; PGI-S, Patient Global Impression of Severity; SHBG, sex hormone-binding globulin; UA, urinalysis; UDI-6, Urogenital Distress Inventory; V, visit.

- a This visit is a telephone call.
- b Height will be measured at screening only.

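### On its most natural reading, the 7-day diary window in section 6.2.1 can reject a Week 12 diary that was kept exactly as instructed

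*Combined protocol and SAP*

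**What the plan says.** Section 6.2.1 sets the validity rule: "each 3-day voiding diary must be recorded within 7 days on either side of a planned visit, based on the date of randomization". The diary covers 3 consecutive days.

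The instruction for the Week 12 diary is given at Week 8 (section 6.1.5): "The subject will be instructed to complete a 24-hour pad weight and 3-day voiding diary within the week preceding her next study visit". Table 12-1 (section 12.1) allows each visit from Visit 2 to Visit 8 to move by 3 days in either direction.

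Section 7.1 scores a missing Week 12 diary as non-response and then adds: "Rules for recording valid diary data are presented in Section 6.2.1". Section 7.7.1 repeats the scoring for the primary analysis: "Subjects who have missing diary data for the screening period or the Week 12 visit will be counted as non-responders for this analysis". On detailed methods, section 7.7 says: "Before unblinding, a separate SAP will be finalized, providing detailed methods for all endpoints".

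**The concern.** Two rules fix when a Week 12 diary is kept, and they use different reference points. The instruction to the woman is tied to her next visit, which can move. The validity rule is tied to the randomization date, which cannot. When the visit is early, the week in which she is told to keep the diary starts before the validity window opens.

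A woman in that position has followed every instruction. If her diary is then set aside as invalid, and so treated as missing, she counts as a non-responder on the primary endpoint even if her leakage fell by well over half. The text also leaves two questions open: what a planned visit is, and whether all 3 diary days or only some must lie in the window. Two programmers could score the same diary differently.

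**Working it through.** The plan gives no figure on this point to reproduce, so the check is a count of days.

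**Inputs**
- Randomization is at Visit 1 (section 6.1.2), and section 7.7 numbers baseline as Day 0. Week 12 is therefore Day 12 × 7 = 84.
- Validity window (6.2.1), read around the target day: 84 − 7 = 77 to 84 + 7 = 91.
- Permitted visit days (Table 12-1): 84 − 3 = 81 to 84 + 3 = 87, which is 7 days.
- A diary is 3 consecutive days (6.2.1) in the week before the visit (6.1.5). For a visit on day v, that week is taken as days v − 7 to v − 1.

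**Compliant positions.** The diary can start on any day from v − 7 to v − 3, so there are 5 starts per visit day and 7 × 5 = 35 positions. The latest possible diary day is 87 − 1 = 86, so the upper limit of 91 never matters. A position fails only if the start is before Day 77.

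| Visit day | Week before | Compliant starts | Starts before Day 77 | Diary days outside |
|---|---|---|---|---|
| 81 | 74–80 | 74–78 | 74, 75, 76 | 3, 2, 1 |
| 82 | 75–81 | 75–79 | 75, 76 | 2, 1 |
| 83 | 76–82 | 76–80 | 76 | 1 |
| 84–87 | 77–83 to 80–86 | 77–81 to 80–84 | none | – |

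The total is 3 + 2 + 1 = 6 of 35. One position lies wholly outside (visit Day 81, diary Days 74–76), two have 2 days outside and three have 1 day outside. The offsets are the same for Week 4 (Day 28) and Week 8 (Day 56), so the counts are too.

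**How far the count depends on the reading**

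| Reading of 6.2.1 | Failing positions |
|---|---|
| Target Day 84, all 3 days inside | 6 of 35 |
| Same, with the week counted as the visit day and the 6 days before it | 3 of 35 |
| Target Day 84, any overlap is enough | 1 of 35 |
| 7 days either side of the whole visit window: 81 − 7 = 74 to 87 + 7 = 94 | 0 of 35 |
| 7 days either side of the actual visit | 0 of 35 |

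**Check of the remedy.** Suppose every diary in the 7 days before an in-window visit is accepted in addition to the existing window. All 35 positions are then valid by construction, and nothing accepted now is lost.

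A replacement rule behaves differently. Take one that requires all 3 days inside Days 77–91 or inside the week before the visit. Days 77–91 admit starts 77 to 89, which is 13.
- Against the any-overlap reading (starts 75 to 91, 17 in all): (17 − 13) × 7 visit days = 28. Five of these are readmitted by the week-before clause, so 23 visit/start pairs are lost and 1 is gained.
- Against Days 74–94 (starts 74 to 92, 19 in all): (19 − 13) × 7 = 42. Six are readmitted, so 36 are lost and none gained.

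**The case against.** The mismatch needs several things at once: the window must be centred on the target day, the visit must be 1 to 3 days early, and the diary must fall at the early end of the preceding week. If the planned visit means the windowed or the actual visit, it disappears. This stands as a limit on the point. It does not remove it, because the only clue to the meaning is the clause tying the rule to the randomization date, and that clause favours the target day.

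The separate SAP may settle the visit windows. That is possible, but its text is not in the document reviewed, and section 7.1 sends the reader to 6.2.1. Section 4.2.2 says that all collected data will be used in the analysis. That is a general statement and does not say how a diary outside the window is scored.

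A reader might infer more than the text supports, in four ways:
- *That about a sixth of women are affected, since 6/35 is 17%.* The positions are not equally likely, and the protocol gives no distribution of visit days or diary starts.
- *That a loss of power can be stated.* This needs the share of women misclassified, which has no source in the protocol.
- *That the handling of an invalid diary is undefined.* The sentence in 7.1 on valid data directly follows the one on missing data, so the ordinary reading is that an invalid diary supplies no Week 12 data.
- *That the rule also invalidates early screening diaries, because it covers each diary.* Inclusion criterion 7, section 6.1.1.2 and Table 12-1 time that diary separately, and section 6.1.2 reviews it for eligibility at Visit 1: "The results of the 24-hour pad weight test and the 3-day voiding diary will be reviewed, and continued eligibility for enrollment will be evaluated".

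**Conclusion.** The point holds as a minor one. On the reading that the wording favours, the validity window does not contain every diary that the protocol tells women to keep: 6 of 35 calendar positions at Week 12 are partly or wholly outside. Confidence in the day counts is high.

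The consequence for the primary endpoint rests on three assumptions: the window is centred on Day 84, all 3 days must lie inside it, and an invalid diary is treated as missing. The first is favoured by the text, the second is left open, and the third is implied by section 7.1. If any overlap is enough, only the diary on Days 74–76 before a Day 81 visit is at risk.

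The number of women affected is probably small and cannot be derived from the protocol. Nothing ties early visits or early diaries to treatment arm, so the effect is equal across arms in expectation. It would be at most a slight dilution of the treatment difference, and the text gives no ground for expecting a bias in favour of either arm.

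**What to change.** In section 6.2.1, keep the existing window and add that a post-baseline diary is also valid if it was kept within the 7 days before an actual visit held inside its 3-day window. State in the same place whether all 3 diary days must lie in the window.

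The change takes a sentence or two and needs no new data. It should be made before unblinding, so that no diary is accepted or rejected with knowledge of the results. Worded as an addition, it removes no diary that the current rule accepts. The choice on the 3 days should be made knowingly: requiring all 3 inside Days 77–91, apart from the added clause, would drop some diaries that are valid under the looser readings.

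The downside is that a few diaries starting as early as Day 74 would count as Week 12. They do not overlap the Week 8 window (56 − 7 = 49 to 56 + 7 = 63). Because the added clause applies only to visits inside their window, it does not turn a diary from a much earlier withdrawal visit into Week 12 data.
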